### **3.2 Secondary**

### **3.3 NON-NIVOLUMAB/DARATUMUMAB COHORTS**

- To characterize the pharmacokinetics of nivolumab when administered as a single agent, nivolumab and ipilimumab when administered in combination, and nivolumab and lirilumab when administered in combination.

- To assess the preliminary antitumor activity of monotherapy nivolumab, the combination of nivolumab and ipilimumab, and the combination of nivolumab and lirilumab in subjects with relapsed/refractory hematologic malignancy.
- To characterize the immunogenicity of nivolumab when administered as a single agent, nivolumab and ipilimumab when administered in combination, and nivolumab and lirilumab when administered in combination.
- To assess the potential association between PD-L1 expression on tumor cells by immunohistochemistry and clinical efficacy measures

#### NIVOLUMAB/DARATUMUMAB COHORTS

- To assess the minimal residual disease (MRD) status for MM subjects in each treatment regimen group
- To assess overall response rates (ORR) and duration of response (DOR) for MM subjects in each treatment regimen group
- To assess progression free survival (PFS) for MM subjects in each treatment regimen group
- To characterize the immunogenicity of nivolumab when administered in combination with daratumumab
- To characterize the pharmacokinetics of nivolumab when administered in combination with daratumumab

[REDACTED]

#### 4 ENDPOINTS

##### 4.1 Primary

The primary objective to characterize the safety and tolerability of nivolumab monotherapy and combination therapy will be measured by the following endpoints:

- Number and percent of subjects that experience drug-related grade 3-4 AEs occurring up to 100 days after the last dose of study drug. [Time Frame - On a continuous basis up to 100 days after the last dose of study drug];
- Number and percent of subjects that experience drug-related grade 3-4 SAEs occurring up to 100 days after the last dose of study drug. [Time Frame - On a continuous basis up to 100 days after the last dose of study drug];
- Number and percent of subjects with clinical laboratory abnormalities by worst toxicity grade by NCI CTCAE version 4.0. [Time Frame - On a continuous basis up to 100 days after the last dose of study drug].

## 4.2 Secondary

### 4.2.1 Pharmacokinetics

The following pharmacokinetic parameters of nivolumab, ipilimumab, and lirilumab, will be derived from serum concentration time profiles of subjects and used to measure the secondary objective related to pharmacokinetics at time points specified in section 5.1 of the protocol:

**Cmax** - Maximum observed serum concentration

**Tmax** - Time of maximum observed serum concentration

**Cmin** - Serum concentration achieved at the end of dosing interval (trough concentration)

**AUC(0-T)** -Area under the plasma concentration-time curve from time zero to the last time of the last quantifiable concentration

**AUC(TAU)** - Area under the concentration-time curve in one dosing interval

**Ceofinf** - Serum concentration achieved at the end of study drug infusion

### 4.2.2 Efficacy

The secondary objective relating to efficacy is to assess the preliminary antitumor activity of monotherapy nivolumab, the combination of nivolumab and ipilimumab, the combination of nivolumab and lirilumab across select relapsed or refractory hematologic malignancies. This objective will be measured by tabulations of individual BOR and analyses of the ORR, duration of response, Progression Free Survival Rate (PFS Rate), and Progression Free Survival (PFS). The BOR outcomes will be based on the disease specific criteria (specified in Appendices 1, 2, and 5 of the protocol) for lymphoma, Cutaneous T-Cell and MM, respectively. Response will be based on efficacy assessments per section 5 of the protocol.

Following protocol amendment 10 which allowed for radiological images to be collected for independent central review, subjects with cHL receiving monotherapy nivolumab were retrospectively evaluated by an IRRC (2007 IWG criteria). Unless otherwise specified, the efficacy endpoints will be derived based on both investigator assessment per the International Workshop to Standardized Response Criteria for Lymphoma per protocol appendix 1 and IRRC assessment according to the 2007 IWG criteria. The investigator-based efficacy endpoints would

be the primary efficacy endpoints, and the IRRC-based efficacy endpoints would be the secondary efficacy endpoints.

In addition, the preliminary antitumor activity of nivolumab in combination with daratumumab will be evaluated in subjects with relapsed/refractory MM in Cohorts A and B. This endpoint will be measured by MRD, ORR, DOR and PFS in each treatment regimen group.

### **Best Overall Response (BOR)**

The Investigator-reported BOR is defined as the investigator determined best response designation over the study as a whole (or at specific landmark interim analyses), recorded between the date of first dose and the date of objectively documented progression, whichever occurs first. The Investigator-reported BOR is captured in CRF form.

The IRRC-assessed BOR for cHL nivolumab monotherapy patients is defined as the best response designation recorded between the date of first dose and the date of initial documented progression per the 2007 IWG criteria or the date of subsequent anticancer therapy, whichever occurs first. Allogeneic SCT and ASCT will be considered as subsequent anticancer therapy. For subjects without documented progression or subsequent anticancer therapy, all available response designations will contribute to the BOR determination. For subjects who continue treatment beyond progression, the BOR should be determined based on response designations recorded up to the time of the initial 2007 IWG defined progression. The IRRC-assessed BOR is applicable only to cHL subjects receiving nivolumab monotherapy.

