8.3.2 Secondary Endpoint(s)

8.3.2.1 Efficacy

The secondary objective relating to efficacy is to assess the preliminary antitumor activity in the combination of nivolumab and daratumumab in subjects with relapsed/refractory MM. This objective will be measured by minimal residual disease status (MRD), objective response rate (ORR), duration of response (DOR), and progression-free survival (PFS) for MM subjects in each treatment regimen group.

Minimal Residual Disease (MRD) in the Nivolumab/Daratumumab Cohorts

Both cytometry and molecular MRD from bone marrow aspirate will be evaluated.

The time point for MRD negative status for MM subjects in the nivolumab/daratumumab cohorts is a dichotomized variable for quantifiable MRD detection.

The first MRD negativity status is defined as the first negative status designation over the study as a whole, recorded between the date of first dose and the last efficacy assessment prior to subsequent therapy.

The best MRD negativity status is defined as the best status designation with the minimum MRD levels over the study as a whole, recorded between the date of first dose and the last efficacy assessment prior to subsequent therapy.

Objective Response Rate (ORR)

Best overall response (BOR) is defined as the best response designation over the study as a whole, recorded between the date of first dose and the last efficacy assessment prior to subsequent therapy.

Objective response rate is defined as the proportion of subjects who had a BOR of either partial response (PR) or complete response (CR) divided by the number of treated subjects (or response-evaluable subjects).

Duration of Objective Response (DOR)

The duration of response is defined as the time when the measurement criteria are first met for objective response until the date of documented disease progression or death, whichever occurs first. For subjects who neither progress nor die, the duration of response will be censored at the date of their last disease assessment.

Progression Free Survival (PFS)

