### **Progression Free Survival (PFS)**

The primary definition of PFS is defined as the time from the date of first dose of study medication to the date of first confirmed disease progression or death, or the time between date of randomization and the date of first documented progression or death for nivolumab/daratumumab cohorts. Subjects who remain alive and have not progressed will be censored on the last adequate tumor assessment date on or prior to the date of subsequent therapy. Allogeneic SCT and ASCT will be considered as subsequent therapy. Subjects who did not have any post-baseline efficacy assessment and did not die will be censored on the date of first dose of study medication or date of randomization for nivolumab/daratumumab cohorts.

The secondary definition of PFS (ITT definition) is defined as the time from the date of first dose of study medication to the date of first disease progression or death, or the time between date of randomization and date of progression or death. Subjects who remain alive and have not progressed will be censored on the last adequate tumor assessment date. Subjects who did not have any post-baseline efficacy assessment and did not die will be censored on the date of first dose of study medication or date of randomization for nivolumab/daratumumab cohorts.

For MM subjects, an adequate tumor assessment visit for ruling out progression will require the following information: Serum monoclonal paraprotein results, if measurable at baseline and Urine monoclonal paraprotein results, if measurable at baseline, or for subjects who do not have measurable serum and urine monoclonal paraprotein results, serum free light chain results, if measurable at baseline.

Sensitivity analyses will be performed based on an alternate censoring scheme to account for non-uniform and infrequent tumor assessment schedules. For this analysis, subjects will be censored on their last visit date, defined as the last date of dosing, tumor assessment or lab assessment, whichever occurs last.

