**Table 1: Censoring Scheme for Primary and Sensitivity Analysis PFS**

Situation	Primary	Sensitivity
No progression per response criteria, no death and no subsequent anticancer therapy	Censored on the date of last tumor assessment	Censored on the date of last visit date
No progression per response criteria, no death and with subsequent anticancer therapy	Censored on the date of last tumor assessment prior or on the date of initiation of the subsequent anticancer therapy	Censored on the date of last visit prior or on the date of initiation of the subsequent anticancer therapy
Progression per response criteria without a subsequent anticancer therapy started	Event on the date of the first documented tumor progression per response criteria	Event on the date of the first documented tumor progression per response criteria
Progression or death after a subsequent anticancer therapy started	Censored on the date of last tumor assessment prior or on the date of initiation of the subsequent anticancer therapy	Censored on the date of last visit prior or on the date of initiation of the subsequent anticancer therapy
Death without progression per response criteria and without subsequent anticancer therapy started	Event on the date of death	Event on the date of death

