### Duration of Response

Duration of response will be only calculated for subjects with best overall response of objective response defined as above. The duration of response is defined as the time between the date of first documented objective response and the date of first documented disease progression, or death, whichever is earlier. Subjects who remain alive and have not progressed will be censored on the last adequate efficacy assessment date prior to subsequent cancer therapy. Allogeneic SCT and ASCT will be considered as subsequent therapy.

Sensitivity analyses will be performed based on an alternate censoring scheme (same as PFS censoring scheme) to account for non-uniform and infrequent tumor assessment schedules. For this analysis, subjects will be censored on their last visit date, defined as the last date of dosing, tumor assessment or lab assessment, whichever occurs last.

Duration of response will be evaluated for responders (PR or CR for lymphoma subjects; SCR, CR, VGPR, or PR for myeloma subjects) only.

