### **Time to Response (TTR)**

Time to response is defined as the time from date of first dose of study medication or date of randomization for nivolumab/daratumumab to the date of the first documented objective response. Time to response will only be evaluated in subjects with minimal objective response of PR.

Time to best response is defined as the time from date of first dose of study medication or date of randomization for nivolumab/daratumumab to the date of the best overall response.

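### The SAP ends the investigator BOR window at progression only, while the protocol and the SAP's parallel rules stop at subsequent therapy; probably a dropped clause, with an effect on ORR that may be nil

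*SAP*

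**What the plan says.** **Investigator BOR.** SAP section 4.2.2 takes the best designation "recorded between the date of first dose and the date of objectively documented progression, whichever occurs first". It adds: "The Investigator-reported BOR is captured in CRF form".

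**Protocol BOR.** Section 8.3.2.1 takes the best designation "recorded between the date of first dose and the last efficacy assessment prior to subsequent therapy". The 01-Oct-2015 protocol text for the earlier cohorts has the same definition in its section 8.3.2.1. Neither has a progression cut-off.

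**Parallel rules in SAP section 4.2.2.**
- The independently reviewed (IRRC) BOR for classical Hodgkin lymphoma (cHL) ends at progression "or the date of subsequent anticancer therapy, whichever occurs first".
- The MRD-negativity windows carry the same pair of end dates.
- Primary PFS is censored at subsequent therapy. Table 1 has a row for "No progression per response criteria, no death and with subsequent anticancer therapy", so the plan expects such subjects. On transplant, the PFS text says "Allogeneic SCT and ASCT will be considered as subsequent therapy".
- For DOR, subjects alive without progression "will be censored on the last adequate efficacy assessment date prior to subsequent cancer therapy".

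**Use of BOR.** ORR is built from BOR and, for the nivolumab/daratumumab cohorts, divided by randomized subjects (SAP section 4.2.2). SAP section 7.5 makes ORR in those cohorts investigator-assessed only.

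**Assessments after a switch.** Protocol sections 3.5.1 and 5.4.1.2 keep myeloma assessments going after a new anti-myeloma therapy starts, until progression.

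**Confirmation.** Protocol sections 3.1 and 5.4.1.2 require each response to be confirmed on a second consecutive assessment before any new therapy begins.

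**The concern.** The SAP and the protocol give different windows for the same secondary endpoint. The SAP sentence closes by asking for the first of several dates but supplies one. The neighbouring IRRC and MRD definitions use the same construction with both dates, which points to a lost clause and not to a deliberate choice.

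The gap falls where data will exist. Myeloma subjects who change therapy before progressing are still assessed every 4 weeks, and no central review of response sits behind the investigator's BOR in these cohorts. Under the SAP wording alone, a first response recorded on the next therapy would count towards ORR for the randomized regimen. The primary DOR of that subject, if alive without progression, would then be censored before the response began. A subject already in partial response before the switch could move to a better BOR category, but ORR would not change.

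**Working it through.** **1. Where each rule stops**

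| Rule | Stops at progression | Stops at subsequent therapy |
|---|---|---|
| Investigator BOR, SAP 4.2.2 | yes | not stated |
| BOR, protocol 8.3.2.1 (both texts) | not stated | yes |
| IRRC BOR, SAP 4.2.2 | yes | yes |
| MRD status, SAP 4.2.2 | yes | yes |
| Primary PFS, SAP 4.2.2 and Table 1 | event | censored |
| Primary DOR, SAP 4.2.2 | event | censored |

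Investigator BOR is the only SAP rule in this list without a subsequent-therapy limit.

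**2. The plan's own ORR figures**

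The protocol synopsis gives lower exact 95% bounds of 31.5% for an ORR of 55% in 20 subjects and 61.5% for 77.5% in 40. The Clopper-Pearson lower bound is the 0.025 quantile of Beta(x, n - x + 1):
- 11/20 = 55%: 31.53%.
- 31/40 = 77.5%: 61.55%.

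Both reproduce, and no stated figure is in dispute.

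**3. Possible shift in ORR**

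The planned 60 subjects at 2:1 give 60 x 2/3 = 40 ND and 60 x 1/3 = 20 D. Let k be the number counted as responders only because of a post-switch response. The shift is 100k/n points. The documents do not give k, so the values below are assumptions.

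| k (assumed) | ND, n=40 | D, n=20 |
|---|---|---|
| 0 | 0 | 0 |
| 1 | 2.5 | 5 |
| 2 | 5 | 10 |

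Taking such subjects out of the plan's illustrative results lowers the exact bound as follows:
- D: 11/20 gives 31.5%, 10/20 gives 27.2%, 9/20 gives 23.1%.
- ND: 31/40 gives 61.5%, 30/40 gives 58.8%, 29/40 gives 56.1%.

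**4. Consequence for DOR**

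DOR is censoring date minus first-response date. Suppose a first response after the switch were counted in a subject alive without progression. The censoring date is the last adequate assessment before the switch, and the response falls at least one 28-day interval later. DOR is then nominally -28 days or lower. If a partial response is first seen at the last assessment before the switch and only confirmed afterwards, the two dates coincide and DOR is about 0. Under the protocol's confirmation rule neither case is a confirmed response.

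**The case against.** The strongest reply is that the protocol already closes the gap for myeloma. Sections 3.1 and 5.4.1.2 require confirmation before any new therapy, and SAP section 4.2.2 bases response on assessments under protocol section 5, which brings that rule in. Continued assessment after a switch runs until progression and does not relax it. On that reading a response first seen after a switch cannot be a confirmed partial response or better. What remains is the risk of a CRF entry that follows the SAP window instead of the protocol.

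Most of this stands, and it is why the effect may be nil. It does not repair the definition. The BOR paragraph does not cite the confirmation rule, and BOR is taken as entered on the CRF. The SAP's other pointer sends myeloma criteria to protocol Appendix 5, whereas the protocol places them in Appendix 3.

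A second objection also stands: adding the missing date does not make the SAP match the protocol, because the protocol has no progression cut-off. In the earlier cohorts, where treatment beyond progression was allowed (01-Oct-2015 text, section 3.1.2), a response after progression could count under the protocol but not under the SAP.

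A reader might infer that reported ORR will be inflated, or that the investigator and IRRC results in cHL are biased against each other. The documents support neither. They give no count of affected subjects. For cHL the two written windows differ, but the documents do not say whether assessments continued after a switch.

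**Conclusion.** The mismatch in wording is certain; an effect on results is not. This is a minor drafting defect in the definition underlying a secondary endpoint, in a cohort that both documents say is not powered for hypothesis testing. Power, type I error and sample size are untouched.

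For myeloma ORR the effect is nil if confirmation before new therapy is enforced on the CRF BOR. If it is not, each affected subject adds 2.5 points in ND or 5 points in D, assuming the planned 40 and 20 subjects. The 5- and 10-point figures for two subjects, and the negative DOR, illustrate what following the SAP wording alone would do; they are not predictions. No effect is claimed for the cHL cohort.

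**What to change.** In the BOR paragraph of SAP section 4.2.2:

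1. End the investigator window at the earlier of documented progression or start of subsequent therapy, as the SAP's MRD definitions do.
2. Count autologous and allogeneic transplant as subsequent therapy, as the IRRC BOR, PFS and DOR rules do.
3. Cite the confirmation rule in protocol section 5.4.1.2 for myeloma.
4. Keep BOR investigator-reported, but check its date against the start of subsequent therapy. Where it falls later, use the best confirmed response recorded on or before that start, obtained by CRF query or from visit-level responses. A subject with a confirmed partial response before the switch then stays a responder.
5. State that the progression cut-off is an addition to protocol section 8.3.2.1, which has none in either text.

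The cost is a few sentences, a date check and possibly some queries. For the nivolumab/daratumumab cohorts both dates are already needed: time to best response runs "to the date of the best overall response", and PFS censoring uses the subsequent-therapy date. SAP section 7.5 plans time to best response for those cohorts only, so a BOR date may have to be obtained for the older ones. Relative to the current SAP wording, ORR can only stay the same or fall.

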### **Progression Free Survival Rate (PFS Rate)**

The PFSR is defined as the probability of a subject remaining progression free or surviving to time  $t$ , where  $t = 6, 12, 18$  and  $24$  months. This probability will be calculated by the product limit method (Kaplan-Meier estimate) which takes into account censored data.

### **Progression Free Survival (PFS)**

The primary definition of PFS is defined as the time from the date of first dose of study medication to the date of first confirmed disease progression or death, or the time between date of randomization and the date of first documented progression or death for nivolumab/daratumumab cohorts. Subjects who remain alive and have not progressed will be censored on the last adequate tumor assessment date on or prior to the date of subsequent therapy. Allogeneic SCT and ASCT will be considered as subsequent therapy. Subjects who did not have any post-baseline efficacy assessment and did not die will be censored on the date of first dose of study medication or date of randomization for nivolumab/daratumumab cohorts.

The secondary definition of PFS (ITT definition) is defined as the time from the date of first dose of study medication to the date of first disease progression or death, or the time between date of randomization and date of progression or death. Subjects who remain alive and have not progressed will be censored on the last adequate tumor assessment date. Subjects who did not have any post-baseline efficacy assessment and did not die will be censored on the date of first dose of study medication or date of randomization for nivolumab/daratumumab cohorts.

For MM subjects, an adequate tumor assessment visit for ruling out progression will require the following information: Serum monoclonal paraprotein results, if measurable at baseline and Urine monoclonal paraprotein results, if measurable at baseline, or for subjects who do not have measurable serum and urine monoclonal paraprotein results, serum free light chain results, if measurable at baseline.

Sensitivity analyses will be performed based on an alternate censoring scheme to account for non-uniform and infrequent tumor assessment schedules. For this analysis, subjects will be censored on their last visit date, defined as the last date of dosing, tumor assessment or lab assessment, whichever occurs last.

**Table 1: Censoring Scheme for Primary and Sensitivity Analysis PFS**

Situation	Primary	Sensitivity
No progression per response criteria, no death and no subsequent anticancer therapy	Censored on the date of last tumor assessment	Censored on the date of last visit date
No progression per response criteria, no death and with subsequent anticancer therapy	Censored on the date of last tumor assessment prior or on the date of initiation of the subsequent anticancer therapy	Censored on the date of last visit prior or on the date of initiation of the subsequent anticancer therapy
Progression per response criteria without a subsequent anticancer therapy started	Event on the date of the first documented tumor progression per response criteria	Event on the date of the first documented tumor progression per response criteria
Progression or death after a subsequent anticancer therapy started	Censored on the date of last tumor assessment prior or on the date of initiation of the subsequent anticancer therapy	Censored on the date of last visit prior or on the date of initiation of the subsequent anticancer therapy
Death without progression per response criteria and without subsequent anticancer therapy started	Event on the date of death	Event on the date of death

